If the catheter and/or tip are retained (intentionally or unintentionally) during the initial procedure or any subsequent procedures, the Subject will be followed for 30 days from the date of the initial procedure to assess any adverse events ascribed to the study procedure or the retained catheter or tip. For Subjects where surgical resection of the Onyx™ cast and retained catheter tip is not undertaken or is incomplete and the catheter and/or tip are retained (intentionally or unintentionally), the Subject will also complete a 12-month follow-up visit to assess safety. Once a Subject has completed the study procedures, all ongoing adverse events will be followed until resolution or until event has stabilized.	

PROTOCOL SYNOPSIS

Sponsor:	Protocol Number: NV-APL001
Micro Therapeutics, Inc. d/b/a ev3 Neurovascular [name]	Revision: A, 05-Aug-2014
	Product: Apollo™ Onyx™ Delivery Micro Catheter
	Regulatory Class: Class III
	Development Phase: Phase IV

Study Flowchart:

PROTOCOL SYNOPSIS	
Sponsor: Micro Therapeutics, Inc. d/b/a ev3 Neurovascular [name]	Protocol Number: NV-APL001
	Revision: A, 05-Aug-2014
	Product: Apollo™ Onyx™ Delivery Micro Catheter
	Regulatory Class: Class III
	Development Phase: Phase IV

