Sponsor: Micro Therapeutics, Inc. d/b/a ev3 Neurovascular [name]	Protocol Number: NV-APL001
	Revision: A, 05-Aug-2014
	Product: Apollo™ Onyx™ Delivery Micro Catheter
	Regulatory Class: Class III
	Development Phase: Phase IV
Sample Size Justification (con't): In order to ensure a sufficient number of cases for long-term follow-up, the expectation is that with 161 subjects enrolled there will be approximately 16 to 26 subjects with 1-year follow-up. The basis of this estimate is that approximately 50% to 80% of the subjects will have the tip retained by design and approximately 20% of these subjects will not undergo surgery and shall be followed for 1-year. Any retained catheter bodies will be followed. Relative to the precision of the estimates with 16 subjects followed for 1 year, if the incidence of composite primary endpoint events is zero or 1, the exact upper 1-sided Clopper-Pearson 95% limit would be 17.07% and 26.40%, respectively. If the incidence of composite primary endpoint events with 26 subjects was zero or 1, the exact upper 1-sided Clopper-Pearson 95% limit would be 10.88% and 16.98%, respectively.	

TABLE OF CONTENTS

1	INTRODUCTION	15
1.1	Purpose	15
1.2	Background and Significance	15
1.2.1	Clinical Background	15
1.2.2	Current Brain AVM Treatment Options	15
1.3	Clinical Study Experience	17
1.3.1	Randomized Controlled Trial of Onyx™ LES vs. NBCA	18
1.3.2	BRAVO Registry	18
1.4	Rationale of Clinical Study	19
1.4.1	Study Population	19
1.4.2	Single-Arm Study Design	20
1.4.3	Conclusion	20
2	DEVICE DESCRIPTION	20
2.1	Intended Use	20
2.2	Device Name	20
2.3	Device Description	20
2.4	Device Labeling	21
2.5	Device Tracking	21
2.6	Devices and Equipment	22
3	STUDY OBJECTIVES	22
3.1	Primary Composite Endpoint (30 days)	22
3.2	Acute Secondary Endpoints (30 days)	22
3.3	Long-Term Secondary Endpoints (12 months)	22
4	STUDY DESIGN.....	23
4.1	Study Design and Projected Timeline	23
4.2	Number of Sites and Subjects	23
4.3	Study Population	23
4.4	Subject Selection Criteria	23
4.4.1	Inclusion Criteria	23
4.4.2	Exclusion Criteria	24
5	STUDY PROCEDURES.....	25
5.1	Overview of Study Flow	25
5.2	Informed Consent and Privacy	26
5.3	Screening	26
5.3.1	Schedule of Assessments	26
5.4	Baseline Evaluation	27
5.4.1	Imaging	27

5.4.2	Concomitant Medications	27
5.5	Screen Failure	28
5.6	Enrollment	28
5.7	Pre-Embolization	28
5.8	Embolization Procedure	28
5.8.1	Device Use	28
5.9	Post-EMBOLIZATION Discharge	28
5.10	Surgical Resection	29

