5.3.1 Schedule of Assessments

An overview of the assessments to be performed is provided in Table 1.

Table 1. Schedule of Assessments

Assessment	Baseline (-30 days)	Pre- Embolization	Embolization Procedure	Post- Embolization Discharge or +24 hours post- embolization	Surgical Resection	30 Day Follow-up ¹ (+/-7 days)	12 Month Follow-up ² (+/-42 days)
Informed Consent	♦						
Inclusion/Exclusion	♦						
Demographic Characteristics	♦						
Medical History	♦						
Brain AVM characteristics	♦						
Physical Exam	♦						
Neurologic Exam	♦						
Barthel Index		♦		♦		♦	♦
Modified Rankin Scale (mRS)		♦		♦		♦	♦
National Institutes of Health Stroke Scale (NIHSS)		♦		♦		♦	♦
Imaging	•	♦	♦	♦	♦	♦ ³	♦
Embolization Procedure Information and Device Usage or Surgical Resection			♦	♦	♦		
Technical Events			♦				
Concomitant Medications	•	♦	♦	♦	♦	♦	♦
Adverse Events			♦	♦	♦	♦	♦

1. 30 day follow-up will occur 30 days after surgical resection, or 30 days after initial embolization if resection is not done.

2. Only for Subjects with catheter and/or catheter tip retention. If the Subject has had multiple embolization procedures, the 12-month visit will take place 12 months after the initial embolization procedure.

3. Subjects with catheter and/or catheter tip retention, or based on physician assessment.

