5.10 Surgical Resection

Some Subjects may undergo complete or partial surgical resection of their AVM. Information about the surgical resection procedure, imaging, concomitant medications, and AEs as defined in Section 6.1 will be collected (see Table 1). Data regarding the degree of resection and catheter retainment will be captured.

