5.11 Follow-up Evaluations

5.11.1 30-Day

Subject who underwent surgical resection will complete a 30-day visit 30 days after surgical resection. For Subjects not undergoing surgical resection, the 30 day visit will be performed 30 days after the initial study embolization. Table 1 describes a list of assessments that will be performed at this visit. Subjects with a retained catheter/tip will undergo imaging at this time point. Subjects experiencing AEs may undergo imaging per physician discretion. Subjects not experiencing an AE and in whom no part of the catheter was retained will complete the study. Subjects experiencing an AE and in whom no part of the catheter was retained will continue to be followed up until AE resolution.

5.11.2 12-Month

Subjects in whom a catheter and/or tip were retained will have a 12-month study visit. If the Subject has had multiple embolization procedures, the 12-month visit will take place 12 months after the initial embolization procedure. If the Subject is experiencing ongoing AEs at 12 months, the Subject will be followed until resolution of the AE. The clock will only reset, if during re-treatment the catheter tip detaches in a non-target location and is not resected. Final imaging will be required at this visit. Table 1 describes a list of assessments that will be performed at this visit.

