8.2 Imaging Core Laboratory

For Subjects in whom the catheter or catheter tip is retained, 30-day, and 12-month imaging will be obtained to assess potential catheter tip migration. Thirty-day imaging will also be collected if it is performed as a result of physician discretion.

Any subsequent imaging obtained as standard of care during participation in the study will be documented on the eCRFs and may be collected.

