9.2.6 Analysis of Secondary Endpoints

For acute and long-term secondary endpoints, descriptive statistics will be provided. Event rates based on Subject count and device count will be provided.

The incidence of catheter and / or tip retention following any deployment of the study device will be summarized using counts, percentages, and 2-sided 95% exact binomial confidence intervals.

Separately, the incidence of catheter and tip retention by the number of deployments of the study device will be summarized using counts, percentages, and 2-sided 95% exact binomial confidence intervals. This tabulation assumes that each procedure / deployment is a separate trial. The intra-subject rate of catheter and tip entrapment will be summarized using descriptive statistics and tabulated by the number of events and the number of deployments.

In order to ensure a sufficient number of cases for long-term follow-up, the expectation is that with 161 subjects enrolled there will be approximately 16 to 26 subjects with 1-year follow-up. The basis of this estimate is that approximately 50% to 80% of the subjects will have the tip retained by design and approximately 20% of these subjects will not undergo surgery and shall be followed for 1-year. Any retained catheter bodies will be followed. Relative to the precision of the estimates with 16 subjects followed for 1 year, if the incidence of composite primary endpoint events is zero or 1, the exact upper 1-sided Clopper-Pearson 95% limit would be 17.07% and 26.40%, respectively. If the incidence of composite primary endpoint events with 26 subjects was zero or 1, the exact upper 1-sided Clopper-Pearson 95% limit would be 10.88% and 16.98%, respectively.

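### The 12-month tip-migration rate has no at-risk denominator, so under the general rule in 9.2.1 it is diluted by Subjects and devices with no tip in place

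*Combined protocol and SAP*

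**What the plan says.** **Denominator.** Section 3.3 lists migration of the detached tip as a 12-month endpoint. Section 9.2.1 sets one counting rule and says that it covers primary and secondary endpoints: Subjects with an event over N, where N is the size of the analysis population. It adds a device-based rate over all devices deployed. Section 9.2.2 defines two populations, ITT and FAS, and neither requires a retained tip. For the long-term endpoints, 9.2.6 asks for descriptive statistics with Subject and device counts and names no denominator for migration. Section 3.3 also defines incidence per embolization completed in the study. It calls migration a rate and does not say whether that definition applies to it.

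**Who is seen at 12 months.** The synopsis (Follow-up) limits the visit by resection status: "For Subjects where surgical resection of the Onyx™ cast and retained catheter tip is not undertaken or is incomplete", with the catheter or tip retained. Three other places mention retention only:
- 5.11.2: "Subjects in whom a catheter and/or tip were retained will have a 12-month study visit"
- Table 1, footnote 2: "Only for Subjects with catheter and/or catheter tip retention"
- 8.2: "For Subjects in whom the catheter or catheter tip is retained, 30-day, and 12-month imaging will be obtained"

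**Projection.** Section 9.2.6 expects 16 to 26 Subjects with one-year follow-up out of 161, because "approximately 50% to 80% of the subjects will have the tip retained by design and approximately 20% of these subjects will not undergo surgery". The synopsis (Sample Size Justification) gives the same basis.

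**The concern.** A tip that was never left behind, or that has been fully resected, cannot migrate at 12 months. Many Subjects without a tip will not be seen then at all. Section 5.11.1 says: "Subjects not experiencing an AE and in whom no part of the catheter was retained will complete the study", and for them that happens at the 30-day visit. Keeping them in N treats them as observed without migration.

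Long-term safety of a retained tip is a stated purpose of the study (1.4 and 2.4). A rate that falls as more tips are removed, or as fewer are left behind, does not describe the risk to a patient who carries one.

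The visit rule is a smaller matter. If sites read retention as the state when embolization ends, a Subject whose tip was later removed completely would still owe a 12-month visit and imaging. If they read it as the state after surgery, that Subject would not.

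**Working it through.** **Inputs.** 161 Subjects and an estimated 322 catheters (4.2); 13% attrition (9.1); 50% to 80% with a tip retained, and 20% of these without surgery (9.2.6).

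**The plan's own figures.**
- 161 × 0.50 × 0.20 = 16.1 and 161 × 0.80 × 0.20 = 25.8, which match 16 and 26.
- The one-sided 95% Clopper-Pearson limit is the 0.95 quantile of Beta(x+1, n−x). With n = 16 it gives 17.07% (x = 0) and 26.40% (x = 1). With n = 26 it gives 10.88% and 16.98%. All four match 9.2.6. The plan quotes them for composite primary endpoint events, so they do not set a denominator for migration.

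**One migration at 12 months, by denominator.**

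| Denominator | n | 1/n | One-sided 95% upper limit |
|---|---|---|---|
| ITT, maximum enrollment | 161 | 0.62% | 2.91% |
| FAS, if all attrition falls outside it (161 × 0.87 = 140.1) | 140 | 0.71% | 3.34% |
| Tip unresected, upper projection | 26 | 3.85% | 16.98% |
| Tip unresected, lower projection | 16 | 6.25% | 26.40% |

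On 161 Subjects the rate is understated by a factor of 161/26 = 6.2 to 161/16 = 10.1.

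**Incomplete resections.** The projection counts only Subjects without surgery, whereas the synopsis also keeps those incompletely resected. Their share s among operated Subjects is not in the documents. The cohort is 161 × (0.50 to 0.80) × (0.20 + 0.80s):
- s = 0: 16.1 to 25.8
- s = 5%: 19.3 to 30.9
- s = 10%: 22.5 to 36.1
- s = 20%: 29.0 to 46.4

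At the assumed 20%, one migration reads 1/46 = 2.2% to 1/29 = 3.4%, still 3.5 to 5.6 times the figure on 161.

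**Device rate.** One event over 322 catheters is 0.31%. The proper comparison is with retained tips in place, whose number the plan does not give. If each of the 16 to 26 Subjects had one such tip, the rate would be 6.3% to 3.8%. If each had two (32 to 52 tips), it would be 1/32 = 3.1% to 1/52 = 1.9%. One or two tips per Subject is an assumption.

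**Tip ever retained.** 161 × 0.50 = 80.5 and 161 × 0.80 = 128.8. On 80 to 129 Subjects one migration reads 1.3% to 0.8%. These Subjects were at risk of migration for some time, though not all of them up to 12 months.

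**The case against.** **The denominator is not laid down for migration by name.** Section 9.2.1 opens with adverse event reporting, gives its denominators by way of example, and 3.3 speaks of the detached tip, which could imply a rate among detached tips. It stands that 9.2.6 nowhere prescribes a wrong denominator for this endpoint. But 9.2.1 expressly includes the secondary endpoints and defines N, and nothing overrides it. The per-embolization wording in 3.3 adds a competing candidate; it does not settle the matter.

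**A denominator restricted to tips still in place loses information.** A tip later resected was at risk until removal and may have been removed because it moved. This stands, and the fix therefore needs a second summary over tips ever retained.

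**The rate can be recomputed.** Counts are shown with the percentages, listings are planned, and 5.10 states: "Data regarding the degree of resection and catheter retainment will be captured". That limits the harm, but the reported rate should not need repair by its reader.

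**The visit rules may already agree.** A reader might infer that 5.11.2 contradicts the synopsis and raises the 12-month cohort from 16 to 26 to some 80 to 129 Subjects. The documents do not support that as the expected result. The synopsis states the resection condition outright, 5.10 records retainment at resection, and 5.11.1 places the 30-day visit of operated Subjects after surgery. All of this favors judging retention after surgery, and 5.11.2 is then close to the synopsis. Some ambiguity remains because 9.2.6 uses the word for the state before surgery. The study flow figures are not reproduced in the text available, so they cannot settle it.

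**Conclusion.** The denominator point holds. As written, the general rule puts Subjects and devices with no retained tip into the 12-month migration rate. One event reads 0.6% on 161 Subjects and about 3.8% to 6.3% on the projected 26 to 16 with an unresected tip. The size rests on the plan's retention and surgery shares and on full enrollment. If up to 20% of operated Subjects are assumed to keep a tip, the at-risk figure falls to between 2.2% and 3.4%, and the conclusion is unchanged.

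The visit-rule point holds only as a need to align wording. The count of 80 to 129 applies only if retention means status before surgery.

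Nor should a reader infer a threat to the study's success criterion. Migration is descriptive, with no hypothesis attached, and the primary test uses 30-day composite events.

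**What to change.** 1. In 9.2.6, define the 12-month migration rate among Subjects with a tip or catheter still in place after any resection and followed to 12 months. For the device-based rate, use the retained tips or catheters meeting the same conditions. State that this overrides 9.2.1, and the per-embolization definition of incidence in 3.3, for this endpoint.
2. Also in 9.2.6, report migration seen at any time before resection over all Subjects, or tips, with a tip ever retained. Tips removed after moving are then not lost.
3. In 5.11.2, Table 1 footnote 2 and the 12-month clause of 8.2, add the synopsis condition that there was no resection or only a partial one. Leave the 30-day imaging rule in 5.11.1, footnote 3 and 8.2 as it is.

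The cost is protocol and SAP wording. Section 5.10 already collects degree of resection and retainment, and 9.2.5 already splits the primary endpoint by whether the tip was resected, so no new data item is needed. The drawback is a smaller denominator and a less precise 12-month rate: with one event in 16 Subjects, the one-sided 95% upper limit is 26.40%.

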5.12 New Information

Study Subjects will be informed of new information as it becomes available during the course of this study. Subjects will be notified, at a minimum, in accordance with the IRB's procedure for providing updated information to clinical study Subjects.

5.13 Termination of Subject Participation

Subjects may withdraw from the study at any time without penalty or loss of medical care, or they may be withdrawn at any time at the discretion of the PI or Sponsor for safety or administrative reasons (such as early termination of the study by the Sponsor).

5.13.1 Subject Withdrawal

All enrolled Subjects have the right to withdraw their consent at any time during the study. Data collected until the time of withdrawal will remain in the study database and may be used during analysis. Whenever possible, the site staff should obtain written documentation from the Subject that wishes to withdraw his/her consent for future follow-up visits and contact. If the site staff is

unable to obtain written documentation, all information regarding the Subject's withdrawal must be recorded in the Subject's medical record. In addition, the appropriate eCRFs must be completed for the Subject and clear documentation of the Subject's withdrawal be provided to the Sponsor.

5.13.2 Subject Discontinuation by Investigator

An Investigator may discontinue a Subject from the study, with or without the Subject's consent, for any reason that may, in the Investigator's opinion, negatively affect the well-being of the Subject. If a Subject is withdrawn from the study, the Investigator will promptly inform the Subject and Sponsor.

5.13.3 Lost to Follow-Up

A Subject will be considered lost to follow-up if the Subject cannot be reached after three attempts; attempts can include telephone, email and registered letter. These failed contact attempts will be documented on the eCRF. Every effort should be made to maintain contact with the Subject during the study.

5.14 Deviations to the Investigation

A protocol deviation is defined as an event where the Investigator or study personnel did not conduct the study according to the clinical protocol. Deviations shall be reported to the Sponsor regardless of whether medically justifiable or taken to protect the Subject in an emergency.

Except a change that is intended to eliminate an immediate hazard to a Subject, the protocol will be followed as described. Subject specific deviations and non-Subject specific deviations will be reported. Investigators will also adhere to procedures for reporting study deviations to their IRB in accordance with their specific IRB reporting policies and procedures.

Sites with a high rate of protocol deviations will be closely evaluated and are expected to implement corrective action to prevent further deviations. If a site demonstrates persistent deviations, as described above, the site may be terminated.

Some information collected in this study is not essential to the study endpoint and will not be considered a deviation if absent.

5.14.1 Discontinuation by IRB

The IRB may choose to discontinue the Study at any center(s) for which they granted approval if:

- The research study is not conducted in accordance with the IRB's requirements.
- The research study indicates unexpected serious harm to Subjects.

The Investigator needs to report to the Sponsor within 5 working days a withdrawal of approval by the reviewing IRB (21 CFR 812.150).

5.14.2 Study Discontinuation by Sponsor

The Sponsor may choose to discontinue the study should the Sponsor discover additional information during the study that may cause harm to Subject safety.

If the study is terminated prematurely or suspended, the Sponsor will promptly inform all clinical Investigators of the termination or suspension and the reason(s) for this. The IRB will also be informed, either by the Sponsor or Investigator if a local IRB is utilized, promptly and provided with the reasons(s) for the termination. If applicable, regulatory authorities will be informed. Enrolled Subjects will be asked to complete all remaining study visits and the Subjects will then be seen by the treating physician according to standard patient care following AVM treatment.

6 ADVERSE EVENTS

The following AEs will be collected during the course of the study on the eCRFs:

- All Serious Adverse Events (SAEs)
- All Device-related Adverse Events
- All Procedure-related Adverse Events
- All AEs with an underlying neurological cause (Neurological Adverse Event)

See Section 6.1 for event definitions and categorizations. The status of the AEs will be evaluated throughout the study. AEs will be collected from the point of enrollment in the study until a Subject exits the study. Investigators must obtain all information available to determine the causality, location with respect to the vascular territory catheterized, and outcome of the AE and to assess whether it meets the criteria for classification as a serious and/or unanticipated device event requiring expedited notification to the Sponsor, regulatory agency, and IRB (if applicable) within the specified reporting timeframe.

All study AEs, as well as the treatment and follow-up required, should be documented in the Subject's medical records and in the eCRF. All study AEs will be followed by the Investigator until resolution. A list of potential anticipated AEs is provided in Section 10.2.

6.1 Event Definitions

An *Adverse Event (AE)* is defined as any untoward medical occurrence, unintended disease or injury, or untoward clinical signs (including abnormal laboratory findings) in Subjects, users or other persons, whether or not related to the investigational medical device. (ISO 14155:2011)

Note 1: This includes events related to the investigational device or the comparator.

Note 2: This includes events related to the procedures involved (any procedure in the clinical investigational plan).

Note 3: For users or other persons this is restricted to events related to the investigational medical device.

An *Adverse Device Effect (ADE)* is defined as an adverse event related to the use of an investigational medical device. (ISO 14155:2011) The investigational medical device for this study is the Apollo™ micro catheter.

Note 1: This includes any adverse event resulting from insufficiencies or inadequacies in the instructions for use, the deployment, the implantation, the installation, the operation, or any malfunction of the investigational device.

Note 2: This includes any event that is a result of a use error or intentional misuse.

A *Serious Adverse Event (SAE)* is defined as an AE that:

- a) Led to death,
- b) Led to serious deterioration in the health of the Subject, that either resulted in
 - a. A life-threatening illness or injury, or
 - b. A permanent impairment of a body structure or a body function, or
 - c. In-patient or prolonged hospitalization, or
 - d. Medical or surgical intervention to prevent permanent life-threatening illness or injury or permanent impairment to a body structure or a body function,
- c) Led to fetal distress, fetal death or a congenital abnormality or birth defect (ISO 14155:2011)

Note 1: This includes device deficiencies that might have led to a serious adverse event if a) suitable action had not been taken or b) intervention had not been made or c) if circumstances had been less fortunate. These are handled under the SAE reporting system.

Note 2: A planned hospitalization for pre-existing condition, or a procedure required by the Clinical Investigational Plan, without a serious deterioration in health, is not considered to be a serious adverse event.

A *Serious Adverse Device Effect (SADE)* is defined as an adverse device effect that has resulted in any of the consequences characteristic of a serious adverse event. (ISO 14155:2011)

An *Unanticipated Serious Adverse Device Effect (USADE)* is defined as a serious adverse device effect which by its nature, incidence, severity or outcome has not been identified in the current version of the risk analysis report. (ISO 14155:2011)

Note: Anticipated: an effect which by its nature, incidence, severity or outcome has been previously identified in the risk analysis report.

An *Unanticipated Adverse Device Effect (UADE)* is defined as any serious adverse effect on health or safety or any life-threatening problem or death caused by, or associated with, a device, if that effect, problem, or death was not previously identified in nature, severity, or degree of incidence in the investigational plan or application (including a supplementary plan or application), or any other unanticipated serious problem associated with a device that relates to the rights, safety, or welfare of Subjects. (21 CFR 812.3)

Severity:

- Mild: No limitation of usual activities, no therapy or only symptomatic therapy required to treat the injury or illness.
- Moderate: Some limitation of usual activities or specific therapy is required.
- Severe: Inability to carry out usual activities, hospitalization, emergency treatment, life threatening events, or death.

Relatedness:

- **Study Disease-related:** Event is clearly attributable to the underlying study disease state with no temporal relationship to the device, treatment, or medication.
- **Concomitant disease-related:** Event is clearly attributable to the underlying concomitant disease state with no temporal relationship to the device, treatment, or medication.
- **Procedure-related:** Event has a strong temporal relationship to the study procedure.
- **Device-related:** Event has a strong temporal relationship to the study device, and alternative etiology is less likely.

- Study device: Apollo™ micro catheter

All events considered "device-related" will be further characterized as either:

- **Anticipated:** When the event was previously identified in nature, severity or degree of incidence in the investigational plan. Or
- **Unanticipated:** When the event was not previously identified in nature, severity or degree of incidence in the investigational plan.
- **Ancillary device-related:** Any device(s) other than the Apollo™ micro catheter used at embolization, such as access devices, delivery micro catheters, non-ionic contrast, guidewires, or any other adjunctive, approved/cleared device for treatment of AVMs.
- **Unknown:** Event relationship cannot be attributed to any of the above categories and remains undetermined.

